Contingency management involved offering rewards contingent initially on attendance and then on negative urinalysis results for cannabis. Following assignment to the contingency management group, participants were introduced to the voucher programme at an initial information and assessment session. Participants were informed that they needed to achieve two weeks of abstinence to return a cannabis free urine. In week 1 of the intervention, participants received a £5.00 voucher for attending and providing a urine specimen independent of the drug test results with the aim of familiarising participants with the urine testing and voucher procedures. From week 2 until week 12 participants earned vouchers contingent upon consecutive negative specimens or specimens that indicated a reduction in cannabis use.

If the participant has a pre-planned holiday or other significant commitment, they were able, on a maximum of two occasions, to suspend the intervention for one week, returning after 2 weeks rather than after 1 week. They were still be expected to show evidence of abstinence

at that point, and they needed to request this suspension no later than at the time of their previous scheduled appointment. The Early Intervention team was also be able to request suspension of the intervention for a maximum of one month if a participant relapsed and lost capacity to decide whether they wished to continue. If capacity was not regained in one month, the intervention was not continued.

Optimised treatment as usual (to be delivered to the intervention and control groups)

Optimised treatment as usual for cannabis was a phase specific, individually tailored, psycho-educational approach to problematic cannabis use for generic early intervention care coordinators that applies general psycho-educational approaches used in first episode psychosis⁴. The full delivery was typically achieved over approximately three hours, normally offered over regularly programmed sessions of 15-30 minutes duration.

Sample size

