Time to relapse defined as admission to hospital, crisis house or crisis resolution team for mental health related problems. Data for this outcome were obtained from the informatics department of the relevant Trusts. This was in the form of the date of admission and which service admitted in the 18 months following baseline. Those that did not have any data recorded were assumed to not have any admissions and their data were censored 18 months after entry into the trial. If a participant died within the follow up period, the study team had this information and follow up will be censored at the date of death if they have did have a relapse before then. Likewise if their drop out date was known, this will be used as the date of censoring. Everything possible was done to trace people who dropped out to ensure that it was ascertained whether they had a relapse and if so when. This is because

drop out may be related to the outcome and therefore introducing informative censoring. [outcome type: time to event]

Secondary Outcomes

Secondary outcomes were measured at 12 weeks and 18 months. Analysis will be separately at these time points to match the clinical question of examining the outcomes at each of these time points rather than over time.

Cannabis positive urine sample at follow up. This will be a dichotomous outcome, positive versus negative.

Positive symptom score using the positive scale of the Positive and Negative Syndrome Scale (PANSS)⁹. This consists of seven items: Delusions, Conceptual disorganization, Hallucinatory behaviour, Excitement, Grandiosity, Suspiciousness and Hostility. Each item is scored on a scale from one to seven with one indicating absent and seven indicating extreme. These are summed to give an overall score which ranges from 7 to 49. [outcome type: continuous]

Negative symptom score using the negative scale of the PANSS. This consists of seven items: Blunted affect, Emotional withdrawal, Poor rapport, Passive-aphathetic social withdrawal, Difficulty in abstract thinking, Lack of spontaneity and flow of conversation, Stereotyped thinking. Each item is scored on a scale from one to seven with one indicating absent and seven indicating extreme. These are summed to give an overall score which ranges from 7 to 49. [outcome type: continuous]

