These will be analysed separately for data collected at 12 weeks and 18 months. Models will include severity of cannabis use at baseline and whether the participant was part of the pilot trial. For the dichotomous outcomes (cannabis positive urine, engaged in work or study), logistic regression with robust standard errors to account for clustering by therapist will be used. If there are too few participants engaged in work or study for logistic regression to be possible then results will be reported descriptively. For continuous outcomes (positive and negative symptoms), linear regression with robust standard errors will be used.

For count outcomes, Poisson regression with robust standard errors will be used for count outcomes (number of cannabis days and number of admissions over follow up). If there are excess zeros for either count outcome, then the use of zero inflated Poisson regression will be explored.

Appropriate estimates and 95% confidence intervals will be presented for all analyses.

Missing data

There is not much missing data for the primary outcome since it is an objective outcome collected from the appropriate informatics departments.

There is missing data for other variables, especially at follow up. This may be because of non-attendance at the follow up appointment or non-response to specific questions. The extent and patterns of missingness will be assessed. Potential predictors of missing values that are related to the outcomes will be identified. .

Multiple imputation¹⁶ may be used if it is felt to be necessary. We will only impute outcome data if surrogate outcomes or variables closely related to the missing outcome(s) are available. Otherwise there is no gain in imputing outcomes¹⁷.

The primary analysis will be complete case analysis with analysis using multiple imputation being a supportive analysis if it is carried out.

Supportive analyses

There will be up to six supportive analyses for the primary outcome:

1. Analysis of all outcomes with their baseline predictors of missingness, that is modelling including the randomised allocation, whether the participant was in the pilot trial and the level of cannabis use at baseline

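### The urine outcome is analysed by complete case, and no committed analysis tests whether giving a specimen depends on the result differently in the two arms

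*SAP*

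**What the plan says.** - **Outcome** (SAP, Secondary Outcomes): "Cannabis positive urine sample at follow up. This will be a dichotomous outcome, positive versus negative". It is measured at 12 weeks and 18 months. No rule is given for a participant who provides no specimen.
- **Model** (SAP, Analysis of the secondary outcomes): a logistic model for urine at each time point, with standard errors made robust to therapist clustering. On covariates: "Models will include severity of cannabis use at baseline and whether the participant was part of the pilot trial".
- **Analysis set** (SAP, Missing data): "The primary analysis will be complete case analysis with analysis using multiple imputation being a supportive analysis if it is carried out".
- **Imputation** (same section): multiple imputation "may be used if it is felt to be necessary", with no trigger stated, and "We will only impute outcome data if surrogate outcomes or variables closely related to the missing outcome(s) are available".
- **Reasons for missing data** (same section): "This may be because of non-attendance at the follow up appointment or non-response to specific questions". A participant who attends but declines to give urine is not mentioned. The extent, patterns and predictors of missingness are to be examined.
- **Supportive analyses**: item 1 covers all outcomes, but only with baseline predictors of missingness. The variables it names (allocation, pilot membership, baseline cannabis level) are already in the main model. Further supportive analyses of secondary outcomes are optional and name 18 months only.
- **Intervention** (SAP, Randomised treatments): "Participants were informed that they needed to achieve two weeks of abstinence to return a cannabis free urine". Week 1 paid for a specimen whatever the result. Weeks 2 to 12 paid for negative specimens or those showing reduced use.

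**The concern.** Reducing cannabis use is a stated aim of the trial. A participant usually knows before the visit whether a specimen is likely to be positive, and that knowledge may affect whether they attend or give one. Complete-case analysis then compares the arms among a selected group. The two arms also had different experience of urine testing: only intervention participants had eleven weeks (weeks 2 to 12) in which payment turned on the result, and nobody was blinded to their own allocation. Willingness to give a specimen when expecting a positive could therefore differ by arm.

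At stake is whether a difference in urine results, or its absence, can be read as an effect on cannabis use. Adjusting for baseline predictors does not address dependence on the unseen result. Standard multiple imputation does so only as far as the variables in the imputation model account for it. Nothing that the SAP commits to would show how far the conclusion rests on that assumption. The gap is widest at 12 weeks, the end of the voucher period, which the optional supportive analyses of secondary outcomes do not name.

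**Working it through.** **Inputs.** The SAP gives no positive rate, specimen rate or power for the urine outcome, so there is no stated figure to reproduce. The target of 544 gives 544/2 = 272 per arm. The only follow-up figure is the pilot's target of at least 60% at three months. All specimen probabilities and true positive rates below are my assumptions.

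**Formula.** Let r+ and r− be the probabilities of giving a specimen when the true result is positive and negative. Within an arm:

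observed odds of a positive = true odds × (r+ / r−)

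so, for the unadjusted odds ratio:

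complete-case OR = true OR × [(r+/r−) in intervention ÷ (r+/r−) in control].

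The bias factor does not involve the true positive rate. It equals 1 whenever r+/r− is the same in both arms, however strongly giving a specimen depends on the result.

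**No true effect (true OR = 1), r− = 80% in both arms:**

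| r+ control | r+ intervention | Complete-case OR |
|---|---|---|
| 60% | 60% | 0.60/0.60 = 1.00 |
| 70% | 65% | 0.65/0.70 = 0.93 |
| 70% | 60% | 0.60/0.70 = 0.86 |
| 75% | 60% | 0.60/0.75 = 0.80 |
| 70% | 50% | 0.50/0.70 = 0.71 |
| 60% | 70% | 0.70/0.60 = 1.17 |

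**On the percentage scale**, for 70% v 60% with 75% truly positive in both arms:
- control: 0.75×0.70 = 0.525 positive and 0.25×0.80 = 0.20 negative, so 0.525/0.725 = 72.4% observed positive;
- intervention: 0.75×0.60 = 0.45 and 0.20, so 0.45/0.65 = 69.2%.

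**False-positive rate.** I used a two-proportion normal approximation, 272 randomised per arm, two-sided 5%, without clustering or covariates. At 75% truly positive, rejection is about 10% for 70% v 60%, about 17% for 75% v 60% and about 6% for 70% v 65%. Stronger differences matter more. At 60% truly positive, control 70% for both results against intervention 60% (positive) and 80% (negative) gives OR (0.60/0.80)/(0.70/0.70) = 0.75 and rejection of about 28%. With 50% and 80% in the intervention arm the OR is 0.625 and rejection about 60%.

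**Missing counted as positive.** The rate becomes 1 − (1 − true rate) × r−. At 60% truly positive, r− = 70% in control and 80% in intervention gives 1 − 0.40×0.70 = 72% v 1 − 0.40×0.80 = 68%. This rule can itself create a difference, so it is a bound and not a replacement analysis.

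**What a sensitivity analysis would have to vary.** In the 70% v 60% example, the odds of a positive among the missing, divided by the odds among those observed, are:
- intervention: (0.30/0.05)/(0.45/0.20) = 6/2.25 = 2.67;
- control: (0.225/0.05)/(0.525/0.20) = 4.5/2.625 = 1.71.

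Only an analysis that lets this ratio differ by arm recovers the true OR of 1.

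**The case against.** A reader might infer that specimen-giving in this trial does depend on the result, and that complete-case analysis will therefore favour the intervention. The SAP supports neither step.

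- **The dependence is not documented.** The SAP attributes missing data to non-attendance and item non-response. Result-dependence is plausible but remains an assumption.
- **Dependence alone does no harm.** It must differ by arm to bias the odds ratio, and the direction is open. Controls also know whether they have used cannabis. Weeks of routine testing, including a paid week 1 whatever the result and payment for reduced use, could make intervention-arm users more willing to give a specimen. Vouchers had long ended by 18 months.
- **The plan is not silent.** It will examine missingness, and its condition for imputing outcomes can be met by self-reported cannabis days, a listed outcome, so it does not rule that information out. Unequal loss of specimens could be seen in the planned summaries.
- **The size is assumed**, and for moderate differences the excess false-positive rate is modest.

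All of this stands and limits the point. It does not close the gap: imputation is optional, describing missingness does not show its effect on the odds ratio, and no analysis for data not missing at random is fixed at either time point.

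**Conclusion.** The point holds in conditional form. Complete-case analysis of urine is exposed to bias if result-dependent specimen-giving differs by arm, and no committed analysis tests for that. Under no true effect, a ten-point difference in users' specimen rates moves the odds ratio to 0.86 or 1.17, depending on which arm withholds more, with rejection of about 10% instead of 5% at 75% truly positive. The larger assumed differences give 0.63 to 0.75. These figures rest on assumed specimen rates, an unadjusted odds ratio and full recruitment. They show what is possible, not what happened.

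This concerns one secondary outcome, though it is the only objective cannabis measure among the outcomes listed. Time to relapse comes from routine data and is not affected. The change is a cheap improvement to the plan; the complete-case model need not be withdrawn.

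**What to change.** Keep the stated complete-case logistic model, and commit to the following at both 12 weeks and 18 months, before allocation is revealed:

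1. **Tabulate missing urine by arm**, split into not interviewed and interviewed without a specimen.
2. **Impute missing urine** using arm, baseline cannabis use and self-reported cannabis days at the same visit, alongside the model's other covariate. Follow-up use is defined as days over 12 weeks or six months, and Time Line Follow Back is listed only at baseline. Classify by use in the last 14 days only if day-level follow-up data exist. Participants who were not interviewed may also lack the self-report, so this step helps mainly those interviewed without a specimen.
3. **Run a not-at-random sensitivity analysis** in which the odds of a positive among the missing, relative to those observed, vary separately by arm. The grid should be wide enough to include values such as the 1.71 and 2.67 above in either arm. Include missing counted as positive as one bound.

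Report whether the urine conclusion is robust across these analyses. The cost is a paragraph of SAP text, one table and a few extra runs on outcomes the trial already lists. The downside is that the urine result may look less certain.

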The CONSORT¹⁻³ flow diagram will be constructed by/in collaboration with the Trial Manager who will have logs of service users who do and do not agree to take part in the study. It will include number of service users randomised to each arm of the trial, and the numbers who have follow up data available.

All analyses will be on an intention to treat basis and data from the pilot trial will be incorporated into the main trial.

Data will be analysed using Stata version 14¹⁵.

Descriptive statistics

Initial analyses will look at summary statistics for all variables, both overall and by randomised group. Summary statistics for continuous variables will be mean, median, SD, lower quartile, upper quartile, minimum and maximum and reported appropriately according to distribution. Summary statistics for categorical variables will be frequency and percentage within each category.

Summary statistics of baseline variables by whether a participant has dropped out of the study will also be examined to determine whether the drop outs had similar characteristics to those who remained in the study at baseline.

Analysis of the primary outcome

The primary outcome will be initially examined using Kaplan Meier survival curves by randomised allocation. If the assumptions of proportional hazards is satisfied, Cox Proportional Hazards modelling to compare the intervention and control groups will be carried out, adjusting for severity of cannabis use at baseline (the stratification variable, dichotomous – 1 to 3 times a week versus 4+ times a week) and whether the participant was part of the pilot trial. If the assumption of proportional hazards is not fulfilled, alternative modelling strategies will be employed. Robust standard errors will be used to account for clustering by therapist; which should account for most of the centre effects in this multicentre individually randomised trial. Hazard ratios and 95% confidence intervals will be presented.

Analysis of the secondary outcomes

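### Read literally, supportive analysis 1 refits the main model, so it would not check missing data for most secondary outcomes

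*SAP*

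**What the plan says.** **Main models.** Under Analysis of the primary outcome, the Cox model compares the arms "adjusting for severity of cannabis use at baseline (the stratification variable, dichotomous", 1 to 3 versus 4 or more times a week), and also adjusts for pilot membership. Under Analysis of the secondary outcomes, "Models will include severity of cannabis use at baseline and whether the participant was part of the pilot trial". The Missing data section makes complete cases the main analysis.

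**Supportive item 1.** The list opens with "There will be up to six supportive analyses for the primary outcome", yet its first item is wider: "Analysis of all outcomes with their baseline predictors of missingness". The definition follows at once: "that is modelling including the randomised allocation, whether the participant was in the pilot trial and the level of cannabis use at baseline". It names no other variable.

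**Other missing-data provisions.**
- The Missing data section says that predictors of missing values related to the outcomes are to be identified. It names none and gives no selection rule.
- Multiple imputation "may be used if it is felt to be necessary". Outcomes are to be imputed only if surrogates or closely related variables are available.
- Number of admissions has a separate list of up to two supportive analyses. One adds predictors of missingness to the main-analysis factors. The other includes participants discharged within 18 months and counts them as having no admissions.
- For secondary outcomes collected at 18 months, the Supportive analyses section says only that further analyses may be done.

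**The concern.** The SAP acknowledges that variables other than the primary outcome have missing values, most of all at follow-up, and gives non-attendance as one cause. A supportive analysis that adds predictors of missingness can show whether a complete-case comparison is sensitive to who was lost. One that refits the main model cannot. Agreement between the two could then be taken as reassurance about missing data when no check had been made.

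The outcomes affected matter. Cannabis use, positive symptoms, and participation in work or education are all named in the trial's aims.

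**Working it through.** The point rests on no figure in the plan, so there is none to reproduce. The check is a comparison of model terms.

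| Model | Terms stated in the SAP |
|---|---|
| Main, primary outcome | allocation; baseline cannabis severity (dichotomous stratifier); pilot membership |
| Main, secondary outcomes | allocation; baseline cannabis severity; pilot membership |
| Supportive item 1, all outcomes | allocation; pilot membership; baseline level of cannabis use |
| Supportive item 1, number of admissions | main-analysis factors plus predictors of missingness |

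**Step 1: compare the terms.** If *level* in item 1 is the variable called *severity* in the main models, the first three rows hold the same set. Only the order differs.

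**Step 2: consequence.** The same model on the same complete cases gives the same coefficient for allocation:

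estimate(item 1) − estimate(main) = 0

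**Step 3: illustration on assumed data, not trial data.** The simulation used 400 runs of 544 participants, a true effect of 0, linear regression on complete cases, and missingness that depended on a baseline variable x in opposite directions in the two arms.

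| Model | Mean estimated effect |
|---|---|
| Main (allocation, severity, pilot) | 1.29 |
| Item 1 as worded (allocation, pilot, severity) | 1.29 |
| Main terms plus x | −0.02 |

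The largest difference between the first two models in any run was about 1e-14, which is rounding error. Adding the real predictor x moved the estimate to about zero. The value 1.29 is a product of the assumed missingness and says nothing about the size of bias in CIRCLE. The illustration shows only that the literal item 1 cannot detect such a bias and that an additive version can.

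**Step 4: what else covers each outcome.**
- Number of admissions: its own additive analysis and a second one for discharged participants.
- Urine result, PANSS positive and negative scores, work or study, and cannabis days: item 1, plus imputation and further 18-month analyses that are only optional.
- Supportive item 2 excludes participants without secondary-outcome follow-up, but it concerns the primary outcome only.

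**The case against.** **The intent was probably additive.** Item 1 speaks of each outcome's own predictors, which sits badly with one fixed list for every outcome. Predictors still to be identified from the data cannot already be listed. The parallel item for number of admissions is plainly additive. This stands as a reading of intent. It does not settle what is to be fitted: items 4 and 5 and the number-of-admissions item all state openly that terms are added, whereas item 1 gives a definition that names only main-model terms. Even on the generous reading, no rule for choosing predictors is given.

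**Level may not mean severity.** Baseline use is also collected by Time Line Follow Back, so *level* could be another variable. The models would then differ, and the identity in Step 2 would fail. The SAP does not say which variable is meant.

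**Stronger readings that the document does not support.**
- A reader might infer that item 1 is the only committed missing-data analysis for the secondary outcomes. Number of admissions is a secondary outcome with two of its own. Item 1 is also no firm commitment, since it stands in a list of up to six headed for the primary outcome.
- A reader might take the pilot's aim of three-month follow-up on at least 60% to mean that 40% missing was acceptable. It is a pilot target and says nothing about tolerated missingness in the main trial or at 18 months.
- A reader might infer that dropout related to baseline cannabis severity goes unadjusted. That variable is already in every main model.

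**Imputation is a separate choice.** The SAP gives a cited reason for imputing outcomes only when related variables exist. That is a fair position. But the SAP describes data that appear to meet its condition: relapse from Trust records, with little missing, and baseline and 12-week measurements. Repairing item 1 alone would not deal with dropout that follows relapse, because relapse occurs after randomisation. Some auxiliaries are weaker than they look: 12-week values may be missing for the same people, and reported cannabis days may be lost along with urine at a missed visit.

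**Conclusion.** The point holds as a drafting defect with a real consequence. Taken literally, and if *level* is the stratifying severity variable, item 1 repeats the complete-case result exactly. That leaves urine result, PANSS scores, work or study, and cannabis days with no listed missing-data model except optional ones. If *level* is some other variable, the model is not a repeat, but the variable is undefined and the baseline predictors are still not specified.

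The main estimates do not change, and nothing in the SAP shows that they are biased. Secondary-outcome missingness is not stated, so the size of any bias cannot be given. The change should be made, but the point concerns supportive analyses only.

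**What to change.** 1. Replace the defining clause of item 1 with the form used for number of admissions: the main-model factors plus the baseline variables found, blind to arm, to predict missingness and to be related to the outcome. State the selection rule. The Blinding section already keeps the statisticians blind until the primary analyses are verified.
2. Move the item out from under the primary-outcome heading to one that covers all outcomes.
3. Commit to one supportive multiple imputation of the 18-month secondary outcomes, using relapse status from Trust records, the baseline value and, where observed, the 12-week value as auxiliaries.

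The cost is a change of SAP wording and modest extra analysis, with no new data. The imputation relies on a missing-at-random assumption, which should be stated with the result. For the logistic and Cox models, adding covariates can itself shift the odds or hazard ratio, so a small difference from the main estimate should not be put down to missing data alone.

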2. Analysis of the primary outcome excluding those participants who have no follow up secondary outcome data (for 12 weeks and 18 months separately) because those who drop out or die may be different to those who remain in the study and/ or survive. Before doing this, some demographic statistics comparing those who remained in the study and those who dropped out will be produced.
3. Analysis of those in the main trial only as some changes were made to the protocol at the end of the pilot before the main trial commenced, which might mean the participants behave differently to those in the pilot trial.
4. Analysis of the primary outcome controlling for the same factors as in the primary analysis plus the number of psychoeducation sessions attended (which is being offered in both arms of the trial).
5. Analysis of the primary outcome controlling for the same factors as the primary analysis and number of admissions in the six months prior to baseline.

6. Analysis of the primary outcome controlling for the same factors as the primary analysis, but using centre as the clustering variable not therapist.

There will be up to two supportive analyses for the number of admissions during follow up:

1. In addition to the factors included in the main analysis, this will include predictors of missingness.

2. Including those who were discharged within 18 months and assuming they had no admissions over the follow up time.

There may be supportive analyses for secondary outcomes collected at 18 months, as outlined in the missing data section.

Exploratory analysis:

We will investigate potential patterns and degree of non-compliance using clinical definitions of compliance and descriptive analysis. We will perform a Complier Average Causal Effect (CACE) analysis if feasible.

There are no subgroup analyses planned.

Health Economic analyses

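### Supportive analyses 4 and 2 of time to relapse condition on events after randomisation, so they cannot serve as plain robustness checks on the primary result

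*SAP*

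**What the plan says.** In the SAP's Supportive analyses section, item 4 for the primary outcome keeps the factors of the primary Cox model and adds a further term: "plus the number of psychoeducation sessions attended (which is being offered in both arms of the trial"). No counting window, landmark time or time-dependent form is given.

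The Randomised treatments section describes this psychoeducation as part of optimised treatment as usual, delivered to both arms. "The full delivery was typically achieved over approximately three hours", and it was "normally offered over regularly programmed sessions of 15-30 minutes duration".

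Item 2 repeats the primary analysis "excluding those participants who have no follow up secondary outcome data (for 12 weeks and 18 months separately"). The stated reason is that "those who drop out or die may be different to those who remain in the study and/ or survive".

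Two other places bear on this. Under Primary Outcome, relapse dates come from the Trusts' informatics departments, not from interviews, and the SAP explains its tracing effort by saying that "drop out may be related to the outcome and therefore introducing informative censoring". Under Statistical analyses it states: "All analyses will be on an intention to treat basis".

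**The concern.** Follow-up for relapse runs for 18 months from baseline. A count of sessions attended builds up over part of that time. If a relapse interrupts the sessions, a person who relapses early has a low count because of the relapse. Entering the final count as a fixed covariate then treats a consequence of the outcome as a predictor of it, which is the immortal-time problem. Where attendance also differs between arms, the false sessions effect passes into the treatment hazard ratio.

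Item 2 raises a different problem. Whether someone gives a 12-week or 18-month interview is decided after randomisation and may depend on relapse. Most relapses in an 18-month follow-up precede the 18-month interview, so that version of item 2 is the more exposed. The people removed generally still have relapse data in the records. The possible difference between drop-outs and those who stay is a reason to keep them in an analysis that does not need the interview.

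At stake is how the primary result is read. Each item could appear to contradict a sound primary estimate or to confirm an unsound one.

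**Working it through.** **Contrast within the SAP's own list.** Item 5 adjusts for admissions in the six months before baseline, a true baseline covariate. Item 4 adjusts for something that happens afterwards. Nothing in the SAP marks the difference.

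**Inputs from the SAP.** Control relapse-free proportion 0.50, intervention 0.65, follow-up 18 months. Under proportional hazards the implied hazard ratio is ln(0.65)/ln(0.50) = 0.62, against 0.63 stated. Three hours is 180 minutes, so sessions of 30 or 15 minutes give 180/30 = 6 to 180/15 = 12 sessions.

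**Inputs that must be assumed.** The delivery window, attendance by arm, and whether sessions stop at relapse. The point rests on no figure stated in the SAP, so the mechanism was checked by simulation: exponential relapse times, 50% control relapse by 18 months, and sessions with no effect on relapse.

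*Item 4, first set.* 544 people, 300 replicates, sessions accruing until the earlier of relapse and 6 months, capped at 6. When sessions stop at relapse, the sessions coefficient is about 0.78 each.

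| Attendance (intervention v control) | True treatment HR | Adjusted HR |
|---|---|---|
| Equal | 1.00 | about 1.00 |
| 10% higher | 1.00 | about 1.06 |
| 0.7 v 0.5 a month | 1.00 | about 1.28 |
| 0.5 v 0.7 a month | 1.00 | about 0.79 |
| 0.7 v 0.5, sessions continue after relapse, no shared cause | 1.00 | about 1.00 |
| 0.7 v 0.5 a month | 0.62 | about 0.79 |

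*Item 4, second set.* 200,000 people, about 8 planned sessions (maximum 12), sessions stopping at relapse.

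| Delivery window | 3 months | 6 months | 18 months |
|---|---|---|---|
| Sessions HR, equal rates | 0.88 | 0.80 | 0.60 |
| True 1.00, equal rates | 1.00 | 0.99 | 0.99 |
| True 1.00, intervention 25% higher | 1.25 | 1.46 | 1.70 |
| True 1.00, intervention 20% lower | 0.84 | 0.74 | 0.62 |
| True 0.63, equal rates | 0.64 | 0.64 | 0.73 |
| True 0.63, intervention 25% higher | 0.78 | 0.92 | 1.30 |

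The second set moves further because more sessions are at issue: 25% of 8 is 2 planned sessions, against (0.7 − 0.5) × 6 = 1.2 in the first set.

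A hand check shows the route of the bias. It is roughly (sessions HR)^−(difference in mean sessions). For the 6-month window with 25% higher attendance, the means are 8.5 and 7.0 and the sessions HR is 0.787, so 0.787^−1.5 = 1.43, close to the simulated 1.46.

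If sessions continue after relapse but attendance and relapse share an unmeasured cause (6-month window, 25% higher attendance), a true 1.00 becomes 1.14.

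*Item 2.* Assumed interview rate 75% in people who do not relapse.

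| Interview rate in relapsers (control / intervention) | True 1.00 | True 0.63 |
|---|---|---|
| 55% / 55% | about 1.0 | about 0.62 |
| 55% / 70% | 1.19 | 0.74 |
| 70% / 55% | 0.84 | 0.52 |

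**The case against.** Both items belong to a list of up to six supportive analyses. No decision rule depends on them, and the primary Cox model keeps everyone randomised and adjusts only for cannabis severity and pilot status. That stands, and it limits the consequence.

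The bias in the treatment hazard ratio is also conditional. Relapse includes crisis-team contact, and care coordinators deliver the psychoeducation, so sessions could continue after a relapse. The weekly visits in the intervention arm are for urine tests and vouchers, so they do not establish that psychoeducation attendance differs. A reader might infer from the 0.7 v 0.5 scenario that item 4 would give false positives nearly half the time (46% to 49% in repeated simulation), or would cut power from about 93% to around 40%. The SAP does not support that as a forecast. It is one unfavourable combination of three unstated inputs.

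A reader might also extend immortal-time bias to item 2. It does not fit there; the problem is selection.

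Item 2 has a sensible motive, since the SAP assumes no admissions for anyone without recorded data. But the exclusion depends on having an interview and not on record coverage, so it removes people with valid relapse data. The planned comparison of drop-outs with those who stayed describes the selection and does not correct it.

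**Conclusion.** The point holds as a fault of specification in two supportive analyses. Item 4 uses a post-randomisation count as a fixed covariate. If sessions stop at relapse, its coefficient is spurious whatever the arms do. The treatment hazard ratio is distorted when attendance differs by arm as well, or when a real treatment effect lengthens the time available for sessions over a long window. It is undistorted if sessions continue after relapse and no shared cause links attendance with relapse. Under a true null the simulated values run from 1.00 to 1.28 or 0.79 in the first set, and further with more sessions or a longer window. The direction cannot be known beforehand from the SAP.

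Item 2 selects on interview status. It is biased when relapse-related loss differs by arm, and nearly unbiased when that loss is equal. Whatever the size, it conflicts with the SAP's statement that every analysis is by intention to treat.

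The primary estimate and the sample size are not touched.

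**What to change.** Item 4: replace it with a description of sessions attended by arm. If a model is wanted, use a time-updated session count, or a landmark analysis with the landmark stated, and label the result non-causal. The planned CACE analysis should not be relied on for this: psychoeducation is given in both arms, so randomisation is no instrument for it, and the SAP does not yet define compliance.

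Item 2: replace it with a sensitivity analysis in all randomised participants that varies the censoring or no-admission assumption for those who dropped out or lack record coverage. Inverse-probability-of-censoring weights built on baseline predictors of drop-out are one option. If item 2 is kept, label it as not intention to treat.

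The cost is SAP wording and one extra analysis, with no new data.
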